1.1 Introduction

Pilonidal disease is a common problem among adolescents and young adults. It affects 26 per 100,000 people with an incidence of 1.1%.^{1,5} It is characterized by the development of epithelialized tracks and sinuses within the natal cleft extending up to the level of the coccyx posteriorly (the area between the buttocks and posterior to the anus). Entrapped hair follicles become infected resulting in acute and chronic wounds and draining sinuses that can incur both short term and long term morbidity, disability, and poor quality of life.² The most often seen initial presentation is that of a painful mass in the sacrococcygeal region.⁷ Initial treatment is usually with antibiotics and/or surgical incision and drainage of the inflamed and often infected cystic cavity. Recurrence rates have been conservatively reported at 16% and as high as 30% in some patient populations.^{2,3}

The morbidity of this disease is very significant. Patients, usually in their adolescence and young adulthood, may endure chronic pain/inflammation, drainage of sinus tracts associated with significant odor, and occasional negative-pressure wound VAC dressings which are cumbersome. When disease is active, these patients must lay prone at all times when attempting to sleep and are unable to sit due to their wounds; patients with recurrent disease report losing months to years of school and work obligations related to the treatment and chronic nature of their wounds as well as the emotional toll related to an embarrassing problem in a sensitive body area. This disease remains a source of frustration for patients and their families; they desire a durable treatment.

For patients with recurrent disease, there are both medical and surgical methods to treat and/or palliate pilonidal disease. Each of these methods incurs a different risk-benefit profile and has been associated with significant morbidity. Overall, surgical methods appear to be more durable with long term success rates ranging from 84 to 89% However, surgical excision and reconstruction of this area can be associated with significant morbidity and cost. Recurrence rates of pilonidal disease after resection have been reported to be 11%, respectively.^{2,3} Furthermore, wound issues after resection with primary closure have been reported to be as high as 30%.⁴ Medical therapy is largely dependent upon continued lifelong hair removal either from shaving or chemical depilation, meticulous hygiene to the area, and recurrent courses of antibiotics with intermittent need for both office-based, and operating room incision and drainage procedures. This approach to pilonidal disease incurs a chronicity that can lead to longer term disability and reduced quality of life. In fact, the presence of pilonidal disease and its complications is an accepted indication for Disability Insurance qualification.⁶ It has been noted by several authors that an optimal treatment for pilonidal disease has yet to be identified.^{2,3}

A small number of studies indicate that laser hair depilation of the natal cleft appears to be protective for pilonidal disease recurrence.⁴ Due to this limited data, the mechanism of this disease, and the absence of randomized controlled data in the alternative treatment modalities of pilonidal disease, we believe that laser depilation should be studied as a first line therapy. The goal of this study is to: 1) assess the safety and patient tolerance of laser depilation through a single arm pilot study, and 2) determine the efficacy of this treatment in a single center

randomized controlled trial comparing laser depilation to standard of care in pediatric patients with pilonidal disease.

1.2 Relevant Literature and Data

Surgical Management of Pilonidal Disease: Studies related to the surgical management of pilonidal disease have largely focused on the technical aspects of resection and reconstruction. Over one hundred studies in the literature have reported various methods for managing this disease, but with inconsistent methodology and consistently unsatisfactory outcomes. The ideal operation for pilonidal disease should eradicate the disease, minimize recurrence, and carry low morbidity and disability. Incision and drainage has been the primary treatment in cases of acute presentation. After incision and drainage overall successful healing has been reported to be approximately 60%, whereas the remaining patients required an additional excision procedure before closure of these wounds. For patients with recurrent disease, wide local excision with primary or secondary closure, with consideration of off-midline closure, has been widely advocated. However, wide local excision in this body region is associated with significant morbidity including a post-operative wound complication rate of 30%. Marsupialization for pilonidal disease entails incising the sinus tracts without excision of normal tissue resulting in smaller wounds, limited tissue trauma, and shorter recovery.⁸ However, reported duration of healing and durability has been variable.

Medical Management of Pilonidal Disease: Standard medical management of pilonidal disease utilizes hair depilation and local wound care with intermittent antibiotic administration for flares.

Phenol solutions have also been tried in an attempt to sclerose sinus tracts. This involves one or more injections into the affected chronic sinus tracts until filled, removal of sinus hairs and debris with forceps, as well as local shaving. Smaller prospective series have demonstrated success rates ranging from 60% to 95%.⁹⁻¹² In cases of recurrent chronic sinus disease, phenol injection and local depilatory cream application on a weekly basis have shown low subsequent recurrence rates (0%–11%) at extended follow-up.¹³ In chemical depilatory creams, common active ingredients are calcium thioglycolate or potassium thioglycolate, which breaks down the disulfide bonds in keratin and weakens the hair so that it is easily scraped off where it emerges from the hair follicle. The hair follicle does remain with hair regrowth noted in 2 to 5 days and there can be some local skin irritation on the site of application. Some studies have explored the utility of certain skin glues to close the chronic tracts associated with chronic pilonidal disease. One such study utilized Fibrin glue been injected into these chronic tracts after simple curettage with some positive effect.¹⁴ Overall, studies of sclerosing agents and glue have yielded variable results with limited long term efficacy.

Laser Depilation in Pilonidal Disease: In several retrospective studies and small prospective studies, laser hair removal has shown promise as an adjunct therapy to decrease recurrent infections and decrease the need for repeat surgery in adults and older adolescents. Lukish et al published a retrospective review of twenty-eight teenage patients with pilonidal disease who underwent initial surgical excision of their presenting abscess. Laser depilation was found to be well tolerated with only one patient presenting with recurrent disease after a mean follow up of 24 months.⁴ Landa et al determined that their series of 6 patients with recurrent pilonidal disease

saw progressive resolution of folliculitis after 3 to 11 treatments with no need for recurrent excision. No complications or recurrence were reported.¹⁷ Schulze et al reported their experience of eighteen men and five women treated with laser depilation from 2001 to 2004. All patients had experienced recurrent folliculitis and had undergone some form of drainage procedure or prior excision. After surgical excision of the affected area, a Vasculite Plus laser was used for the depilation treatments. Each session involved 9 to 12 treatments and the patients underwent an average of two sessions. All 19 of the patients that remain in follow-up report no recurrence of their folliculitis or need for further surgical procedures.¹⁶ These studies show a positive effect with laser depilation in combating recurrent disease. However, there remains a paucity of prospective controlled studies related to this treatment modality with minimal data reported on the effectiveness of laser depilation in children with pilonidal disease. A prospective study of laser hair removal in pediatric patients to assess safety and generate estimates of effectiveness is warranted.¹⁵⁻¹⁷

2. Study Objectives

2.1 Primary Objective

This is a two-phase study:

- (1) Phase One: Determine the safety and tolerance of laser hair depilation of the natal cleft in adolescents with pilonidal disease.
- (2) Phase Two: Perform a randomized controlled trial of laser hair depilation + chemical/mechanical depilation versus chemical/mechanical depilation only to determine outcomes related to recurrence. Recurrence is defined as a new development of pilonidal abscess, folliculitis, or draining sinus after treatment which would require antibiotic treatment, additional surgical incision and drainage or excision.

2.2 Secondary Objective

[figure not shown]
The secondary objective is to compare adverse outcomes, length of stay, days to return to school or work, costs of care and quality of life measures between those that receive laser hair depilation and those that receive mechanical/chemical hair depilation and hygiene recommendations.

3. Investigational Plan

3.1 Study Design

This is a prospective, randomized single-site trial measuring the safety and feasibility of treating children (12-20 years old) with pilonidal disease using laser hair depilation. There will be two cohorts; those who receive laser hair depilation treatments and those that receive only chemical/mechanical depilation. There will be two phases: Phase One – Pilot study to measure safety and tolerance and Phase Two – Randomized control trial to determine efficacy as a treatment of pilonidal disease and as a possible treatment to intervene on future recurrence.

Enrollment:

[figure not shown]

Randomization:

Randomization

Chemical depilation (cream application as directed) or Mechanical depilation (via shaving)

Treatment:

Follow-up:

Surgical clinic or telephone follow up once monthly for one year to assess for tolerance (traditional pain scale 1-10), resolution, recurrence of cellulitis or abscess, or development of chronic sinus requiring surgical excision

8

3.2 Study Duration and Enrollment

3.2.1 Duration of Study and Enrollment

Each patient will be involved in the study for one year. Patients will be brought into Surgery clinic for 1 treatment every 4-6 weeks to obtain a total of 5 treatments. Follow up will occur monthly for one year from the time of initial treatment as we evaluate for tolerance and efficacy.

3.2.2. Total Number of Subjects Projected and Site

A total of 10 children are projected to be enrolled in the first phase of this pilot study. A total of 164 patients are to be enrolled in the second phase of this study. The study will be conducted at Nationwide Children's Hospital (NCH). Study participants will be recruited in Surgery clinic.

Follow-up research visits will be conducted either by phone, at the Surgery clinic of Nationwide Children's Hospital (NCH), or at the Center for Surgical Outcomes Research (CSOR) within the Center for Innovation in Pediatric Practice (CIPP) at the Research Institute at Nationwide Children's Hospital (RINCH).

3.3. Study Population

Children between the ages of 12-20 who are diagnosed with pilonidal disease will be screened for eligibility.

3.3.1 Inclusion Criteria

- English and non-English speaking patients
- All Fitzpatrick skin types
- Age : 12-20 years
- Diagnosis of pilonidal disease

3.3.2 Exclusion Criteria

- History of photosensitivity
- Actively inflamed pilonidal sinus

4. Study Procedures

Screening and Enrollment

During initial contact with a potential subject, a physician-member of the surgical clinic team will assess their eligibility through satisfaction of both inclusion and exclusion criteria. If all eligibility criteria are met, a physician-member of the research team will invite the child and legal guardian to enroll. The physician-member of the research team will then review the written information about the study and answer any questions.

Upon enrollment, study staff will be contacted by the physician-member of the research team who obtained consent/assent. The study staff will then conduct all data collection throughout the study.

Study Procedures: Laser Hair Depilation Group

Treatment Algorithm

Laser group: Once randomized to the laser depilation arm, patients will be brought into Surgery clinic for 1 treatment every 4-6 weeks to obtain a total of 5 treatments. The treatment will consist of an 810 nm (for Fitzpatrick skin types I-IV) or Nd:YAG (for Fitzpatrick skin types V-VI) 28 joule application at auto pulse duration for 400 ms as based on Fitzpatrick skin type classification to be assessed prior to the first treatment visit and confirmed by the trained laser technician. A cooling platform and application of 23% lidocaine cream applied 45 minutes from the treatment will minimize any discomfort associated with the heat of the laser treatments.

Control group: They will also arrive at the surgery clinic to have this body area shaved and will receive an application of 23% lidocaine cream applied 45 minutes before their simulated laser treatment. They will then receive a simulated laser treatment in which the laser is maneuvered as usual but not actually fired. This will allow patients to be blinded to their treatment. If at the end of the trial, laser depilation is shown to be effective, patients randomized to placebo will be offered laser therapy at the conclusion of the trial at no charge.

Topical Anesthetic:

Application of 23% lidocaine cream applied approximately 45 minutes prior to the laser depilation treatments. This will aid in the subsequent tolerance of the laser treatment.

Laser Depilation: The two lasers that will be used in this study (810 nm or Nd:YAG) are both FDA approved for hair removal in all areas of the human body including the back. These lasers are being used for hair removal in the back region for which they have FDA approval; however

they do not have specific approval for pilonidal disease. In discussion with [name], Director of the Drug and Device Development Services at the RINCH, we believe that an IDE is not necessary for this study as we are using an approved device for investigational purposes with non-significant risk. Laser use in this study poses minimal risk to the patient and these minimal risks are similar to the risks associated with hair removal in the back and other regions of the body for which devices are already FDA approved.

Follow-Up:

Initial follow up for the laser depilation group will be performed to assess for tolerance of the laser treatment. This will occur via use of a REDCap database system where patients can report their pain every 6 hours (with the exception of the overnight period from 8pm-8am) for the first 48 hours after their laser hair depilation treatment. Text message reminders will be sent to these patients for them to give us their pain scores. For those with smart phones, we can text them the link to their REDCap survey, and for those without smart phones or without consistent access to the internet, we can receive their pain scores via return text messages from them. Once tolerance is established, patients will return to surgical clinic every month for their laser or placebo visit. After the 5th clinic visit, they will receive a telephone call monthly to assess for any evidence of resolution or recurrence of disease up to 1 year after the completion of the treatments.

5. Statistical Considerations

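### Phase Two eligibility does not exclude earlier laser depilation of the natal cleft or Phase One participation, so previously lasered patients may be randomized to sham, with a probably small loss of power and blinding

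*Combined protocol and SAP*

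**What the plan says.** Section 3.3.1 admits patients aged 12-20, of any language and any Fitzpatrick type, with a "Diagnosis of pilonidal disease". Section 3.3.2 has two exclusions: "History of photosensitivity" and "Actively inflamed pilonidal sinus". The list is not split by phase. Section 4 then applies it directly: "If all eligibility criteria are met, a physician-member of the research team will invite the child and legal guardian to enroll".

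On the two phases, section 3.2.2 says "A total of 10 children are projected to be enrolled in the first phase of this pilot study" and "A total of 164 patients are to be enrolled in the second phase of this study". Both phases recruit from the same surgery clinic at one hospital, and sections 6.3 and 7.3 describe recruitment in identical terms. Phase Two follows if Phase One tolerance is good (section 5.3). Phase Two controls receive a sham in which the device is moved over the area without firing, so that patients are blinded (section 4).

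On durability, section 1.2 describes a retrospective series of 28 teenagers treated with laser after surgery, "with only one patient presenting with recurrent disease after a mean follow up of 24 months". The Phase Two primary endpoint is recurrence at one year (section 5.1). On availability, section 4 says the two lasers "are both FDA approved for hair removal in all areas of the human body including the back".

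On data, section 7.1 gives an illustrative list that includes past medical and surgical history. It does not name laser treatment received outside the study. The follow-up described in sections 3.1 and 4 covers tolerance, resolution, recurrence and chronic sinus.

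**The concern.** Phase Two asks what laser adds to chemical or mechanical depilation. That contrast is cleanest when controls have not had the experimental treatment. As written, a patient who has already had natal cleft laser meets every criterion and may be allocated to sham. If the effect lasts as long as the sponsor's background suggests, it would cover the whole one-year endpoint window, and that control would bring part of the laser benefit into the control arm.

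The sham is also at stake. Patient blinding depends on not being able to tell a fired laser from an unfired one, and a patient with earlier experience may be able to. Recurrence includes folliculitis needing antibiotics (section 2.1), and contact after the fifth visit is by telephone (section 4), so what the patient believes and reports can influence the endpoint.

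Laser obtained elsewhere after randomization is a separate matter. It is a departure from the assigned treatment, not a baseline characteristic. It calls for recording and reporting, not for an eligibility rule.

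**Working it through.** **Inputs.** Control recurrence 20%, laser recurrence 5%, 82 per group, one-sided alpha 0.025, Fisher exact test (all section 5.3). Phase One size 10, Phase Two size 164 (section 3.2.2). The plan states no power.

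**Reproducing the plan's figure.** Exact power is found by enumerating both binomial distributions and summing the probability of every table that the one-sided Fisher test rejects. At 20% versus 5% it is 79.9% with 81 per group and 80.5% with 82 per group. So 82 is the smallest group size that reaches 80%, which I take as the implied target. There is almost no margin above it.

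**Carry-over model.** Suppose k of the 82 controls had earlier laser and recur at 5% (full carry-over), while the laser arm stays at 5%. The average control rate is

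(0.20 × (82 − k) + 0.05 × k) / 82

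and power is recomputed at that rate, treating the control arm as binomial.

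| k | Control rate | Difference | Exact power |
|---|---|---|---|
| 0 | 20.0% | 15.0 points | 80.5% |
| 1 | 16.25/82 = 19.8% | 14.8 points | 79.7% |
| 5 | 15.65/82 = 19.1% | 14.1 points | 76.1% |
| 10 | 14.90/82 = 18.2% | 13.2 points | 71.0% |

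The row k = 5 is what to expect if all 10 Phase One patients re-enrol (10/164 = 6.1% of Phase Two) and split evenly. The row k = 10 puts all ten in the control arm. Under 1:1 allocation that has a chance of about 0.5^10 = 1/1024, so it is a bound and not a forecast.

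**Partial carry-over.** If previously lasered controls keep half the benefit, they recur at 12.5%. Ten of them then give (72 × 0.20 + 10 × 0.125)/82 = 15.65/82 = 19.1%, the same average rate as five with full carry-over.

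**Laser elsewhere.** The documents give no figure, so these shares of controls are assumptions, again with full carry-over:

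| Assumed share | Control rate | Difference | Power at 82 per group | Per group for 80% |
|---|---|---|---|---|
| 5% | 19.25% | 14.25 points | 76.9% | 88 |
| 10% | 18.5% | 13.5 points | 72.9% | 97 |
| 20% | 17.0% | 12.0 points | 63.7% | 117 |

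**The case against.** The strongest reply is that re-enrolment from Phase One, the only route with a number in the documents, is unlikely. Section 3.2.1 has each patient in the study for one year, section 3.2.2 gives separate totals for the phases, and recruitment ends with scheduling a first treatment. That stands as a reason to expect few such patients. It is not a bar, because no visible text says that the groups may not overlap. The enrolment figure in section 3.1 is not shown, so the finding covers the written criteria only.

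Four stronger readings are tempting, and the documents do not support them.

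- A reader might infer a bias that always runs toward no difference. Patients who come back to clinic after laser may be those in whom it failed. They could recur more often than 5%, and the effect on the difference is then unknown.
- A reader might take the 28-patient series as proof that laser alone protects for two years. Those patients first had surgical excision and the series had no control group, so full carry-over is only an upper bound.
- A reader might conclude that the comparison is invalid. Earlier laser is a baseline characteristic that randomization spreads over both arms. The Fisher test keeps its type I error for the population enrolled.
- A reader might say that the data collection cannot reveal laser use. The list in section 7.1 is illustrative, and past medical and surgical history could capture earlier laser. What stands is narrower: laser after randomization is not named among the follow-up items.

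Outside use is also speculative. Device approval does not show that patients of this age have the natal cleft treated. The sham, and the offer of free laser at the end if it proves effective, reduce the incentive for controls to seek it.

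**Conclusion.** The gap is real and the consequence is probably small. Applied as written, the criteria let previously lasered patients be randomized to sham. If the earlier treatment still protects them, the contrast is diluted. Under full carry-over with the laser arm at 5%, power falls by under 1 point for one such control, about 4 points for five, and 9 to 10 points for ten. Anything larger needs laser use outside the study, whose frequency is unknown. The point is still worth acting on, because 82 per group only just reaches an assumed 80% target and because the same patients weaken the sham. The harm is lost power and blinding. It is not type I error inflation, and its direction is not certain.

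**What to change.** For Phase Two, add to section 3.3.2: *previous laser or light-based depilation of the natal cleft, including participation in Phase One*.

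Separately, for laser after randomization, add one yes/no item with a date to the monthly contact and to section 7.1: *laser or light-based hair removal of the natal cleft outside the study*. Keep patients who answer yes in their randomized arm for the primary analysis, and report their number by arm.

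The cost is one exclusion line and one question in contacts that already take place. The downside is that a few patients become ineligible. The sample size does not change: 82 per group and 80.5% power stand when all controls are laser-naive.

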5.3. Sample Size and Power

We anticipate a group of 10 patients to measure laser depilation tolerance. If tolerance is good (>95% the phase 1 patients pain scores < 4 with no deep second degree burns), we will proceed to the phase 2 study. The sample size for phase 2 will be 164 patients. Since the predicted recurrence rate in the control group based on previous studies may be 20% and in the laser group

will be 5%, we would need 82 patients in each treatment group in order to detect this difference at a one-sided alpha of 0.025 using a Fisher exact test.

6. Study Administration

Phase One: Pilot Study

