7.1. Data Collection and Management

Patient data such as age, gender, skin type, length of disease, past medical/surgical history, number/date of treatments, treatment parameters, patient pain scores after laser treatments and within the first 12 hours after treatment, and any subsequent episodes of folliculitis/drainage. This information will be kept by the study team and access restricted to the study team.

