7.2.4. Data safety and monitoring

Tolerance to the laser treatments will be monitored closely, especially in the first 48 hours of the laser hair depilation treatments. Treatments will stop at any point in which the patient reports enough discomfort to terminate therapy. Areas treated will be observed for cutaneous changes including excessive erythema, discoloration, or tenderness. Data will be monitored by research team members daily. They will ensure that all data (clinical data and questionnaires) collected are correctly completed. Any suggestion of an adverse event identified by this person will be discussed with the principal investigator immediately.

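### The 48-hour pain survey is written for the laser group only and names no phase; if used that way in Phase Two, early pain is sought after laser but not clearly after sham.

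*Combined protocol and SAP*

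**What the plan says.** Section 4, Follow-Up, sets up an early pain survey: "Initial follow up for the laser depilation group will be performed to assess for tolerance of the laser treatment". Patients enter scores in REDCap or reply by text every 6 hours, leaving out 8pm to 8am, "for the first 48 hours after their laser hair depilation treatment". Reminders go to the same patients. The paragraph then moves to clinic visits: "Once tolerance is established, patients will return to surgical clinic every month for their laser or placebo visit". It does not say whether the survey belongs to Phase One, Phase Two or both.

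The Phase Two sections return to early pain. Section 7.1 lists "patient pain scores after laser treatments and within the first 12 hours after treatment" among the data to be collected. Section 7.2.4 states: "Tolerance to the laser treatments will be monitored closely, especially in the first 48 hours of the laser hair depilation treatments". Both repeat the Phase One text of 6.1 and 6.2.4.

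Section 5.1 adds that the tolerance endpoints, a pain score consistently below 4 and no deep second degree burn, are assessed in the week following every treatment. Section 7.2.5 counts pain of at least 8 as an SAE due to laser treatment. Section 2.2 makes adverse outcomes a between-group comparison. Controls attend for shaving, lidocaine cream and a simulated treatment, so that patients are blinded (section 4, Control group).

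**The concern.** A comparison of harms between randomized arms is fair only if harms are looked for equally hard in both. Repeated prompting over 48 hours will find pain that a patient might not mention at a monthly contact. If only laser patients are prompted in Phase Two, part of any excess of early pain after laser reflects the asking and not the laser.

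Control patients can also have early pain, since section 1.1 describes pain as a feature of the disease itself. The rate after sham is the natural yardstick for how much early pain the laser causes. It also bears on the relatedness judgement in 7.2.5, which asks whether an event has another reasonable explanation and decides which SAEs go to the IRB within 72 hours. Without the same survey after sham, that yardstick is not clearly collected.

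**Working it through.** The plan gives no rate of early pain and no figure for how completely it would be captured, so the check is mainly a comparison of passages.

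**1. Who is surveyed early?** Section 4 names the laser group and ties the 48 hours to the laser treatment. No section prescribes this survey after a simulated treatment.

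**2. Which phase?**
- For Phase One: the survey's stated purpose is tolerance. Section 2.1 gives safety and tolerance to Phase One and recurrence to Phase Two. Section 3.1 describes the pilot in the same way. Section 5.1 lists the pain endpoint before turning to Phase Two. Section 5.3 makes tolerance the gate: "If tolerance is good (>95% the phase 1 patients pain scores < 4 with no deep second degree burns".
- For Phase Two: section 4 describes the randomized laser and control procedures, and the survey paragraph runs straight on to placebo visits, which exist only in Phase Two. Sections 7.1 and 7.2.4 restate early pain collection and 48-hour monitoring for Phase Two, in terms of laser treatments.
- Result: the text does not settle it.

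**3. What else could capture early pain after sham?**
- Section 3.1 has a monthly pain-scale check that names no arm in the text available. It does not cover the first 48 hours.
- The 12-hour item in 7.1 also names no arm. It could include sham visits, but it follows a reference to laser treatments and sets no schedule.
- The skin check in 7.2.4, "Areas treated will be observed for cutaneous changes including excessive erythema, discoloration, or tenderness", names no arm and does not record pain scores.

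**4. Intensity of the survey.** Count prompts at 6, 12, ..., 48 hours and drop those between 8pm and 8am.
- A 10am visit leaves 4pm, 10am, 4pm and 10am, which is 4 prompts. Visit times off the 8am/2pm grid all give 4.
- An 8am or 2pm visit gives 2 prompts clear of the boundary and 4 on it (two at 8am, two at 8pm). That makes 6 if both boundary hours count, 4 if one does and 2 if neither does.
- If the survey follows each of the 5 treatments, as the timing in 5.1 suggests, a laser patient has 4 × 5 = 20 scheduled early scores (range 2 × 5 = 10 to 6 × 5 = 30). None is clearly scheduled for a sham patient.

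These counts describe effort and do not measure bias.

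**5. Direction of the bias.** Let p be the true rate of early severe pain and c the fraction captured, in laser (L) and sham (S).
- Observed ratio = (p_L × c_L) / (p_S × c_S). If c_L exceeds c_S, the ratio is pushed up, against laser.
- Observed difference minus true difference = p_S(1 − c_S) − p_L(1 − c_L). With near-complete capture after laser this is about p_S(1 − c_S), which cannot exceed p_S.

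The documents give none of these four quantities, so only the direction follows.

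**6. Primary analysis.** Section 5.3 states "we would need 82 patients in each treatment group" for recurrence of 20% against 5% at one-sided alpha 0.025 by Fisher exact test. Exact power is 79.9% at 81 per arm and 80.5% at 82, so 82 is reproduced if 80% power is assumed (the plan states none). Early pain does not enter this calculation.

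**The case against.** The strongest reply is that the survey belongs to Phase One. Its purpose is tolerance, which is the pilot's objective and the gate to the randomized trial, and in a single-arm pilot there is no one else to survey. Sections 7.1 and 7.2.4 repeat Phase One text, and carried-over wording is weak evidence of a deliberate one-arm design. This largely stands. A reader might infer that the sponsor chose to survey only one randomized arm, and the documents do not support that. What remains is that the text never limits the survey to Phase One, and the Phase Two sections mention early pain only in connection with laser treatments.

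A second reply is that no between-arm pain analysis is specified. Section 2.2 does not define adverse outcomes, section 5.2 names no analysis of pain or adverse events by arm, and 7.2.5 frames severe pain as a laser safety event. This also stands as a limit: the bias matters only so far as the comparison in 2.2 includes pain.

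A third reply is that severe pain soon after sham may be rare, because no laser is fired, lidocaine is applied and actively inflamed sinuses are excluded. That may well be so, and the bound in step 5 then makes the absolute distortion small. But the plan would not clearly collect the data to show it.

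Finally, a reader might infer that texts sent to one arm would unblind patients. That would require patients to learn that the other arm receives none, and no section describes such contact. It is a possibility and not a finding.

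**Conclusion.** The point holds conditionally. As written, the 48-hour survey covers the laser group only and its phase is not stated. If it is used in Phase Two in that form, early pain, including the SAE threshold of 8, is actively sought after laser and not clearly after sham. Any between-arm comparison of adverse outcomes that includes pain would tend to be biased against laser, with no matched sham rate to inform relatedness.

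This rests on two assumptions: that the survey or its laser-only wording carries into Phase Two, and that pain is among the adverse outcomes of section 2.2. The size of the bias cannot be derived from the documents, and any ratio quoted for it would only restate an assumed capture rate.

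Two stronger inferences are not supported. One is that sham pain goes wholly unrecorded: the monthly check and the 12-hour item may pick up some of it. The other is that the recurrence result is compromised: the recurrence endpoint and the 82 per arm do not depend on the survey. The change is still worth making, because it is specific and cheap.

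**What to change.** In section 4 (Follow-Up), 7.1 and 7.2.4, state that in Phase Two the same pain survey and reminders, on the same schedule, are used in both arms after each laser or simulated treatment. If the survey as now written is meant for Phase One only, say so in section 4 and still give one early pain schedule for both Phase Two arms.

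Reconcile the three windows now in the text: 12 hours (7.1), 48 hours (section 4 and 7.2.4) and the first week after each treatment (5.1). State that early pain scores, and pain of 8 or more, will be reported by arm.

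The cost is protocol wording, a small survey burden on control patients and some added handling of replies. The survey and the reminder system are already planned.
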